6.4.6 Bone age and metacarpal cortical width assessment

Left postero-anterior (PA) hand/wrist X-ray will be taken at the final visit of Core study (for Group 1) or Visit 8A-Screening visit for Group 2 and at Visit 15/EOS (Month 24) for both Groups to assess bone age. The change in 2nd metacarpal cortical width at Month 24 relative to the respective baseline will be calculated.

If a fracture of the left upper extremity precludes radiographic imaging, (or precluded this X-ray in the Core study for Group 1) then the right hand will be evaluated for this purpose. In this case, the right hand should be imaged at both Visit 8 and at Visit 15/EOS (Month 24). The information will be used in the assessment of bone density.

6.4.7 Pain assessment

A Faces Pain Scale Revised (FPS-R) will be used for this purpose.

Pain will be evaluated at each visit (at office and telephone visit) at the final visit of the Core study (Group 1 only) and first visit of the Extension study (Visit 9), Visits 11, 12, 14 and 15.

6.4.8 Appropriateness of efficacy assessments

Fracture determination by X-ray is the standard endpoint for long-term studies in osteoporosis. However, in studies of 12 months duration, change in BMD has become an acceptable surrogate and has been shown to be a strong indicator of the efficacy of anti-resorptive therapies, including bisphosphonates such as ZOL. Bone marker assessments of change in BSAP, P1NP, TRAP-5b and NTX often parallel the change in BMD over the same time course. NTX and TRAP-5b measure bone resorption while BSAP and P1NP measure bone

formation. In the growing child, height and bone age also indicate the overall effectiveness of an intervention, but in this study, only trends may be observed over the 12 month period. Bisphosphonates are considered effective in managing bone pain, including fracture pain, and the FPS-R is a scale used to measure pain in children.

The efficacy measurements listed above are therefore expected to be appropriate for this study.

6.5 Safety

Safety assessments will consist of:

- monitoring and recording of all adverse events and serious adverse events,
- renal function (serum creatinine and GFR),
- the regular laboratory monitoring of hematology, blood chemistry and urinalysis, regular measurement of vital signs, and
- the performance of physical examinations including oral examinations for exposed bone.

6.5.1 Physical examination

Physical examination, including an oral exam of the gums and roof of the mouth, will be performed at Visits 9, 12 and 15. If the investigator is concerned about the patient's oral health then the patient may be referred to a dentist.

Significant findings made after the start of study drug which meet the definition of an AE must be recorded in the Adverse Event case report form. Significant findings prior to study drug would be entered on the Medical History CRF for Group 2 only.

Tanner staging will be performed at Visit 8 (Group 1 only), Visit 9 (Group 2 only) and the end of the extension study visit (Visit 15/EOS), when applicable.

6.5.2 Vital signs

Measurements will be made of sitting blood pressure and pulse rate at Visits 8 (Group 1 only), 8A (Group 2 only), 9, 12 and 15.

Clinically notable vital signs are defined in [Appendix 1](#).

6.5.3 [REDACTED] weight

Body weight (to the nearest 0.1 kilogram (kg) in indoor clothing, but without shoes) will be performed at Visits 8 (Group 1 only), 8A (Group 2 only), 9, 12 and 15 and recorded on the Vital sign eCRF.

6.5.4 Laboratory evaluations

A central laboratory will be used for analysis of all specimens collected except for ionized calcium and serum creatinine (for exclusion purposes). Details on the collections, shipment of

samples and reporting of results by the central laboratory are provided to investigators in the laboratory manual.

Clinically notable laboratory findings are defined in [Appendix 1](#).

EMLA cream may be used at all blood draws. EMLA Cream is a topical anesthetic which numbs the skin and decreases the sensation of pain. There should be up to three attempts to obtain a serum sample from the patient at any blood draw.

A central laboratory will collect and evaluate blood and urine samples for hematology, biochemistry and urinalysis at Visit 8A (Group 2 only) and Visits 9, 12 and 15.

An additional lab test for renal monitoring will be performed at Visits 9, 10, 12, 13 and 15.

6.5.4.1 Hematology

Hemoglobin, hematocrit, platelet count, red blood cell count (RBC), mean cell volume (MCV), mean cell hemoglobin concentration (MCHC), RBC morphology, white blood cell count (WBC) and differential white blood cell counts.

6.5.4.2 Clinical chemistry

Non-fasting specimens will be obtained for glucose, creatinine, serum urea, uric acid, total protein, SGOT (AST), SGPT (ALT), alkaline phosphatase, sodium, potassium, chloride, phosphorus, magnesium, albumin, total bilirubin, gamma-glutamyl transpeptidase (GGT) and calcium.

Glomerular Filtration Rate (GFR) will be calculated using the Schwartz equation at all visits where serum creatinine will be measured (Visits 8A (Group 2 only) 9, 10, 12, 13 and 15) by the Central Laboratory.

Schwartz Formula to calculate Glomerular Filtration

$GFR (mL/min/1.73 m^2) = k [Height (m)] / Serum Creatinine (mg/dL)$

k = Constant

k=0.41

Specialized (non-fasting) testing for serum 25-hydroxy vitamin D will be performed at Visit 8/8A and Visit 15. Additional local laboratory evaluation of serum ionized calcium will be evaluated in the local laboratory at pre-dose (first infusion). If local serum ionized calcium at Visit 9 is less than the normal range, the infusion must not be given. The patient may retest once at the investigator's discretion. If the serum ionized calcium retest is in the normal range, the patient may be dosed.

Also, local laboratory evaluation of serum creatinine will be performed at Visit 8A (Group 2 only) and Visit 9 for exclusion purposes. If local serum creatinine at Visit 9 is less than the normal range, the infusion must not be given. The patient may retest once at the investigator's discretion. If the serum creatinine retest is in the normal range, the patient may be dosed.

Patients with laboratory tests containing clinically significant abnormal values will be followed regularly until the values return to normal ranges or until a valid reason for the abnormality, other than study drug related adverse event, is identified

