4.2 Exclusion criteria

1. Patients who demonstrated a major protocol violation in the Core study (Group 1 only)
2. Patients for whom the investigator considers participation in the Extension study is not appropriate (Group 1 only).

(For both groups)

3. Hypocalcaemia and hypophosphatemia: any value (age-matched) below the normal range at Visit 8 or 8 A.
4. Vitamin D deficiency (serum 25-hydroxy vitamin D concentrations < 20 ng/mL or < 50 nmol/L) at Visit 8 for Group 1, Visit 8 A for Group 2.
5. Local serum ionized calcium below the normal range at Visit 9.
6. Renal impairment defined as an estimated GFR < 60 ml/min/1.73 m² based on the Schwartz formula at screening Visit 8 or 8 A (in the case of DMD additional methods may have been recorded in the source documents). Serum creatinine above the normal range at Visit 9 (Group 1) or an increase between Visit 8 A and Visit 9 greater than 0.5 mg/dL (44.2 μ mol/L) for Group 2.
7. Uncontrolled symptoms of cardiac failure or arrhythmia
8. Any prior use of bisphosphonates (other than study drug during the Core study for Group 1 only) or sodium fluoride (doses for osteoporosis not for dental hygiene).
9. Current active hyperparathyroidism or hyper/hypothyroidism or during the Core study.
10. New diagnosis of sarcoidosis currently or during the Core study.
11. New malignancy diagnosis currently or during the Core study.
12. History of hypersensitivity to any of the study drugs or to drugs of similar chemical classes.
13. History of primary bone disease (OI, idiopathic juvenile osteoporosis, rickets/osteomalacia).
14. Female patients of child bearing potential are eligible only if they are: (1) not pregnant/non-lactating; (2) are sexually abstinent or are surgically sterile or (3) if sexually active, must be practicing a medically acceptable form of birth control for greater than 2 months prior to screening visit.

- Females of child bearing potential who are sexually active must agree to continue to practice their birth control during the trial and at least 1 year after completing the trial and must consent to a pregnancy test prior to every dose administration and at the End of Study (EOS) Visit.

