		13 yrs/male	(50.0, 84.0)	If within the normal range at baseline, a value outside of normal range along with at least a 15 unit change
		14 yrs/male	(50.0, 85.0)	If within the normal range at baseline, a value outside of normal range along with at least a 15 unit change
		15 yrs/male	(50.0, 86.0)	If within the normal range at baseline, a value outside of normal range along with at least a 15 unit change
		16 yrs/male	(50.0, 87.0)	If within the normal range at baseline, a value outside of normal range along with at least a 15 unit change
		17-20 yrs/male	(50.0, 89.0)	If within the normal range at baseline, a value outside of normal range along with at least a 15 unit change
		12 yrs/female	(50.0, 82.0)	If within the normal range at baseline, a value outside of normal range along with at least a 15 unit change
		13 yrs/female	(50.0, 84.0)	If within the normal range at baseline, a value outside of normal range along with at least a 15 unit change

Laboratory parameter	Units	Age/gender range	Normal range	Criteria for clinically significant change
		14 yrs/female	(50.0, 85.0)	If within the normal range at baseline, a value outside of normal range along with at least a 15 unit change
		15 yrs/female	(50.0, 86.0)	If within the normal range at baseline, a value outside of normal range along with at least a 15 unit change
		16 yrs/female	(50.0, 86.0)	If within the normal range at baseline, a value outside of normal range along with at least a 15 unit change
		17-20 yrs/ female	(50.0, 86.0)	If within the normal range at baseline, a value outside of normal range along with at least a 15 unit change
Heart Rate	bpm	< 12 yrs	(70.0, 130.0)	If within the normal range at baseline, a value outside of normal range along with at least a 15 unit change
		≥ 12 yrs	(50.0, 120.0)	If within the normal range at baseline, a value outside of normal range along with at least a 15 unit change
Clinical Chemistry				
Blood Urea Nitrogen (serum urea)	mg/dL	≤ 20 yrs	(4.0, 24.0)	Outside the normal range
Calcium	mg/dl	> 2 - 20 yrs	(8.4, 10.3)	Outside the normal range
Chloride	mEq/L	≤ 20 yrs	(94.0, 112.0)	Outside the normal range
Creatinine	mg/dl	5 - 7 yrs/ Female	(0.2, 0.5)	Outside the normal range
		> 7- 10 yrs/ Female	(0.2, 0.6)	Outside the normal range
		> 10 - 13 yrs/ Female	(0.3, 0.7)	Outside the normal range
		> 13 - 16 yrs/ Female	(0.4, 0.8)	Outside the normal range
		> 16 - 20 yrs/ Female	(0.5, 0.9)	Outside the normal range
		5 - 7 yrs/ Male	(0.2, 0.5)	Outside the normal range

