### **Laboratory parameters**

The summary of laboratory evaluations will be presented with respect to three groups of laboratory tests (hematology, serum chemistry, and urinalysis).

- Hematology parameters: hemoglobin, hematocrit, platelet count, red blood cell count (RBC), mean cell volume (MCV), mean cell hemoglobin concentration (MCHC), RBC morphology, white blood cell count (WBC) and differential white blood cell counts.
- Serum chemistry parameters: non-fasting glucose, creatinine, serum urea, uric acid, total protein, SGOT (AST), SGPT (ALT), alkaline phosphatase, sodium, potassium, chloride, phosphorus, magnesium, albumin, total bilirubin, gamma-glutamyl transpeptidase (GGT), calcium; and Glomerular Filtration Rate (GFR).
- Urinalysis parameters: amorphous crystals, urine bilirubin, urine blood, calcium oxalate crystals, urine color, urine glucose, urine ketone, urine leukocytes, urine

nitrite, pH, urine protein dipstick, specific gravity, urine urobilinogen, and WBC Casts (Urine) /LPF.

GFR will be calculated using the Schwartz equation at all visits where serum creatinine will be measured (Visits 9, 10, 12, 13 and 15) by the Central Laboratory.

$GFR (mL/min/1.73 m^2) = k[Height (m)]/Serum Creatinine (mg/dL)$ , where  $k=0.41$

Descriptive summary statistics for both baselines, each post-baseline visit, and change from both baselines to each visit will be presented by laboratory test group and core treatment group. Note that if either the baseline or the post-baseline value is missing, then the calculation of change from baseline will also be missing.

Also, shift tables for hematology and serum chemistry will be provided in order to compare a patient's baseline laboratory evaluation relative to each study visit. For the shift tables, the normal laboratory values will be used to evaluate whether a particular laboratory test value is normal, low, or high for each visit value relative to whether or not the baseline value is normal, low, or high. These summaries, including changes from both baselines, will be presented by laboratory test group and core treatment group.

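### As printed, the Schwartz formula (k = 0.41, height in metres) gives a GFR of at most about 4 at normal creatinine, so no child could meet the eligibility limit of 60

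*Protocol*

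**What the plan says.** Protocol section 6.5.4.2 (Clinical chemistry) states that "Glomerular Filtration Rate (GFR) will be calculated using the Schwartz equation at all visits where serum creatinine will be measured", and then prints "GFR (mL/min/1.73 m^2) = k [Height (m)] / Serum Creatinine (mg/dL") with k = 0.41. The SAP section Laboratory parameters has the same expression, "GFR (mL/min/1.73 m^2) = k[Height (m)]/Serum Creatinine (mg/dL"), with the same constant.

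The eligibility rule that depends on it is exclusion criterion 6 in Protocol section 4.2: "Renal impairment defined as an estimated GFR < 60 ml/min/1.73 m² based on the Schwartz formula at screening Visit 8 or 8 A". The Protocol Summary and section 3.6 carry the same limit of 60. Table 13-1 in Appendix 1 lists normal serum creatinine by age and sex, in mg/dL. The lowest lower limit is 0.2 (for example, ages 5 to 7) and the highest upper limit is 0.9 (over 16 to 20 years).

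Neither document corrects the height unit, gives another value of k, or shows a worked GFR.

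**The concern.** A formula with height in metres and a constant of 0.41 has a numerator below 1 for anyone shorter than 2.4 m (1/0.41 = 2.44). Dividing by a creatinine of a few tenths of a mg/dL gives a single-digit GFR. A limit of 60 in the same units is then out of reach.

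GFR has two roles in this trial. It is the renal eligibility gate, which section 3.6 presents as the safeguard against renal injury. The Amendment 3 rationale also cites the need for normal renal function at entry as the reason for dropping the local creatinine before the second infusion. GFR is also a named safety measure (section 6.5) in a study whose primary objective is safety and whose section 9.4.1 singles out renal safety. The SAP summarises GFR at both baselines and at each later visit, with changes from both baselines. A scale error in the defining line therefore reaches both eligibility and the renal tables.

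**Working it through.** **Inputs**
- k = 0.41, height in metres, creatinine in mg/dL: Protocol 6.5.4.2 and SAP Laboratory parameters.
- Eligibility limit of 60 mL/min/1.73 m²: Protocol 4.2, criterion 6.
- Normal creatinine of 0.2 to 0.9 mg/dL over ages 5 to 20: Table 13-1.
- Height: the documents give none. I assume 0.9 to 2.0 m, which is deliberately wide for ages 5 to 19.

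The plan gives no GFR value to reproduce, so the test is whether the printed formula can reach the printed limit.

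**Formula as printed: GFR = 0.41 × height (m) / creatinine**
- Example: 0.41 × 1.30 / 0.5 = 1.07.
- Lowest in the grid: 0.41 × 0.9 / 0.9 = 0.41.
- Highest in the grid: 0.41 × 2.0 / 0.2 = 4.10. This is still short of 60 by a factor of 60 / 4.10 = 14.6.

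**What it would take to reach 60 as printed**
- Creatinine at 1.30 m: 0.41 × 1.30 / 60 = 0.0089 mg/dL or lower.
- Creatinine at 2.0 m: 0.41 × 2.0 / 60 = 0.0137 mg/dL or lower.
- Height at creatinine 0.2 mg/dL: 60 × 0.2 / 0.41 = 29.3 m.

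No plausible height or creatinine gets there.

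**Same constant with height in centimetres**

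Each value is exactly 100 times larger. The heights below are assumed as typical for each age band. The creatinine limits are from Table 13-1, taking the lower of the two sexes' lower limits where they differ.

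| Age (years) | Assumed height | Normal creatinine (mg/dL) | GFR as printed | GFR with height in cm |
|---|---|---|---|---|
| 5–7 | 1.10 m | 0.2–0.5 | 0.90–2.25 | 90–226 |
| >7–10 | 1.30 m | 0.2–0.6 | 0.89–2.67 | 89–266 |
| >10–13 | 1.45 m | 0.3–0.7 | 0.85–1.98 | 85–198 |
| >13–16 | 1.60 m | 0.4–0.8 | 0.82–1.64 | 82–164 |
| >16–20 | 1.70 m | 0.5–0.9 | 0.77–1.39 | 77–139 |

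With centimetres, normal creatinine at these heights always gives a GFR above 60, and the limit starts to separate normal from raised creatinine. At 1.40 m the cut-off is 0.41 × 140 / 60 = 0.957 mg/dL. Using k = 41 with metres gives identical numbers.

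**The case against.** The strongest reply is that the printed line may never be the one used. Both documents name the Schwartz equation and the central laboratory. The natural reading is that the laboratory supplies GFR from its own specification, which is not available here, and the SAP programs only summarise it. For Group 1, the screening GFR comes from Visit 8, the last Core study visit. That visit is not in the list of GFR visits in section 6.5.4.2, so the value may be produced under the Core protocol. A GFR near 1 in every child with normal creatinine would also be noticed at once. Local creatinine at Visit 9, the creatinine criteria in Table 13-1 and the renal adverse event search do not use the formula. Percentage changes and the ranking of patients survive a constant scale factor.

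All of this stands as a limit on actual harm. The documents do not show that any wrong GFR was produced. The 12 patients reported as enrolled at Amendment 3 are no evidence either way, since that amendment added the formula.

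It is also fair to say that the documents do not prove 0.41 right and only the unit wrong. Other constants of similar size would make a limit of 60 workable. Centimetres are an inference: that reading keeps the printed constant and changes only the unit.

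None of this rescues the text. The line is the same in both documents, which makes a PDF reading fault unlikely, and nothing elsewhere overrides it.

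**Conclusion.** The concern holds. The printed formula, the limit of 60 and the protocol's normal creatinine ranges are mutually inconsistent. As written, GFR cannot exceed about 4.1 at normal creatinine, roughly 15 times below the limit, and every child meets exclusion criterion 6. This conclusion needs only a height no greater than 2.0 m.

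The factor of 100 additionally assumes that k = 0.41 was meant for height in centimetres. The finding that normal creatinine then clears 60 rests on the assumed typical heights. It is not universal: at 1.30 m and 0.9 mg/dL, a short older adolescent, the centimetre version gives 59.2.

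Anyone who codes the printed line gets absolute GFR values and absolute changes that are unusable. Because it defines an eligibility criterion and a renal safety measure, it must be corrected.

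**What to change.** In Protocol 6.5.4.2 and the SAP section Laboratory parameters, write GFR = 0.41 × height (cm) / serum creatinine (mg/dL), or keep metres and write k = 41. Before issuing the correction, confirm the constant and the height unit against the central laboratory's specification, since the documents themselves do not settle which element was misprinted. Then check three things:

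- the source and scaling of the GFR used for criterion 6, including Visit 8 values from the Core study for Group 1 and any redraw before Visit 9;
- the programs behind all GFR summaries and changes from baseline;
- the creatinine unit at the point of calculation. The SAP reports laboratory data in SI units, whereas the formula takes mg/dL. By the protocol's own equivalence (0.5 mg/dL = 44.2 µmol/L), the two differ by a factor of 44.2 / 0.5 = 88.4.

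The cost is one line in each document plus a specification check. No new data or visits are needed, and the limit of 60 is untouched.

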criteria	
 2. Prior use of bisphosphonates (Group 2 only) or sodium fluoride (doses for osteoporosis not for dental hygiene). 3. Hypocalcemia and hypophosphatemia: any value (age-matched) below the normal range at Visit 8 or 8A. 4. Vitamin D deficiency (serum 25-hydroxy vitamin D concentrations of < 20 ng/mL or < 50 nmol/L) at Visit 8 (Group 1) or Visit 8A (Group 2). 5. Renal impairment defined as an estimated glomerular filtration rate (GFR) < 60 mL/min/1.73 m² at screening based on the Schwartz formula at Visit 8 or 8 A; a serum creatinine above the normal range at Visit 9 (Group 1) or an increase between Visit 8A and Visit 9 greater than 0.5 mg/dL (44.2 µmol/L) for Group 2. 6. Female patients of child bearing potential are eligible only if they are not pregnant/non-lactating. Females of child bearing potential must be practicing a medically acceptable form of birth control for greater than 2 months prior to screening visit and consent to pregnancy tests during the study.
Study treatment	i.v. zoledronic acid (ZOL446) 5.0 mg/100 mL solution, supplied in a ready-to-infuse plastic bottle
Efficacy assessments	
The efficacy variables will be measured using the following techniques:
 
 • vertebral morphometric fractures • [REDACTED] • DXA measurements • bone marker analysis • [REDACTED] • bone age and metacarpal cortical width assessment • pain assessment
Key safety assessments	Adverse event monitoring, Physical examinations, Monitoring of laboratory markers in blood and urine; and bone safety monitoring.
Data analysis	
Data analyses will be performed separately for the two populations (Group 1 [SAF-1] and Group 2 [SAF-2]), if not otherwise specified.
 
For the patients in Group 2 (SAF-2); only descriptive statistics will be reported for the single treatment arm.

Key words	Osteoporosis, children and adolescents, zoledronic acid, chronic inflammation, Duchenne muscular dystrophy, glucocorticoids

1 Introduction

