5.6.5 Early study termination by the sponsor

The study can be terminated by Novartis at any time for any reason. This may include reasons related to the benefit risk assessment of participating in the study, practical reasons, or for regulatory or medical reasons (including slow enrolment). Should this be necessary, the patient must be seen as soon as possible and treated as a prematurely withdrawn patient. The investigator may be informed of additional procedures to be followed in order to ensure that adequate consideration is given to the protection of the patient's interests. The investigator will be responsible for informing the Institutional Review Board/Independent Ethics Committee (IRBs/IECs) of the early termination of the trial.

6 Visit schedule and assessments

[Table 6-1](#) and [Table 6-2](#) list all of the assessments and indicate with an "X" when the visits are performed.

Patients must be seen for all visits on the designated day, or as close to it as possible. Missed or rescheduled visits should not lead to automatic discontinuation. Patients who prematurely discontinue the study for any reason should be scheduled for a visit as soon as possible, at which time all of the assessments listed for the final visit will be performed. At this final visit, all dispensed investigational product should be reconciled and the adverse event and concomitant medications reconciled on the CRF.

Patients will be contacted for safety evaluations during the 30 days following the last administration of study treatment.

Table 6-1 Group 1 Assessment schedule

	Final visit of Core study		Infusion visit		Tele-phone	Infusion visit		Tele-phone		Notes
Visit	8	8A	9	10	11	12	13	14	15/EOS and TD and/or PSW	Visit 8 is the Core study completion visit. Visit 8A lists the additional assessments which need to be completed for the Extension study. Visits 8 and 8A assessments must be completed on the same day. Visits 8, 8A, and 9 can occur on the same day
Months relative to the Core study (after Visit 9 - Baseline of Extension study)			up to 10 months after V5 (Core study)	10 days after V9	15 (3 months after V9)	18 (6 months after V9)	10 days after V12	21 (9 months after V9)	24 (12 months after V9)	
Obtain informed consent (D) and assent (S)		X								
Inclusion/exclusion criteria (S)		X	X							
Prior/concomitant medications including GCs (D)	X	X	X	X	X	X	X	X	X	

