Adverse events (D)	X	X	X	X	X	X	X	X	X	Any AEs that occur after Visit 8 but prior to first dose of Extension study (Visit 9) will be collected on the AE (e)CRF
Vital signs (D)	X		X			X			X	Pulse rate and blood pressure only
Physical examination (S)	X		X			X			X	Including an oral examination for exposed bone
Tanner staging (D), if applicable	X								X	
Weight (D)	X		X			X			X	
Pain assessment	X		X		X	X		X	X	Pain is assessed using Faces Pain Scale-Revised (FPS-R)
Central laboratory test (hematology, biochemistry including urinalysis)	X		X	X		X	X		X	All patients will have limited blood chemistry assessments, GFR and urinalysis performed at

	Final visit of Core study		Infusion visit		Tele-phone	Infusion visit		Tele-phone		Notes
Visit	8	8A	9	10	11	12	13	14	15/EOS and TD and/or PSW	Visit 8 is the Core study completion visit. Visit 8A lists the additional assessments which need to be completed for the Extension study. Visits 8 and 8A assessments must be completed on the same day. Visits 8, 8A, and 9 can occur on the same day
Months relative to the Core study (after Visit 9 - Baseline of Extension study)			up to 10 months after V5 (Core study)	10 days after V9	15 (3 months after V9)	18 (6 months after V9)	10 days after V12	21 (9 months after V9)	24 (12 months after V9)	
										Visit 10 and Visit 13
Serum creatinine (local lab)			X							For exclusion purposes
Ionized calcium (local lab)			X							Measured pre-dose, (local lab) prior to first infusion of Extension study
Bio-markers (Serum P1NP, NTX, BSAP, Trap-5b)	X		X			X			X	Not required at Visit 9 if it occurs within 30 days of Visit 8
Serum 25 hydroxy vitamin D	X		X						X	
Pregnancy Test	X		X		[X]	X			X	To be performed for females with childbearing potential only [Only for sites where additional safeguards are required: Supervised urine pregnancy test]
i.v. drug administration (zoledronic acid)			X			X				
Dispense calcium and vitamin D, if required		X	X			X				
DXA measurements (lumbar spine, total body and distal femur)	X		X			X			X	Not required if obtained 3 months prior to Visit 9
X-ray	X								X	Lateral thoraco-lumbar spine and postero-anterior left hand/wrist
Study completion	X								X	

S = Source data, D = Database, TD = study treatment discontinuation, PSW = premature patient withdrawal

Table 6-2 Group 2 Assessment schedule

	Screening Visit	Infusion Visit ¹		Tele- phone	Infusion Visit		Tele- phone		Notes

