Visit	8A	9	10	11	12	13	14	15/EOS and TD and/or PSW	Screening period from Visit 8A to Visit 9 should be as close to 28 days as possible, but cannot be longer than 8 weeks
Months relative to the Core study (after Visit 9 - Baseline of Extension study)		28 days from V8A	10 days after V9	3 months after V9	6 months after V9	10 days after V12	9 months after V9	12 months after V9	
Obtain informed consent (D) and assent (S)	X								
Inclusion/exclusion criteria (S)	X	X							
Medical History (D)	X	X							
Prior/concomitant medication, including GCs (D)	X	X	X	X	X	X	X	X	
Vital signs (D)	X	X			X			X	Pulse and blood pressure
Physical examination (S)	X	X			X			X	Including an oral examination for exposed bone
Tanner staging (D), if applicable		X						X	
Weight (D)	X	X			X			X	
Pain assessment		X		X	X		X	X	Pain is assessed using Faces Pain Scale-Revised (FPS-R)
Central laboratory test (hematology, biochemistry including urinalysis)	X	[X]	X		X	X		X	All patients will have limited blood chemistry, GFR and urinalysis performed at Visit 10 and Visit 13. [Visit 9 lab draw only if more than 4 weeks from Visit 8A].
Serum creatinine (local lab)	X	X							For exclusion purposes
Ionized calcium (local lab)		X							Measured pre-dose (local lab) prior to first infusion

	Screening Visit	Infusion Visit ¹		Telephone	Infusion Visit		Telephone		Notes
Visit	8A	9	10	11	12	13	14	15/EOS and TD and/or PSW	
Bio-markers (Serum P1NP, NTX, BSAP, Trap-5b)		X			X			X	
Serum 25 hydroxy vitamin D	X							X	
Pregnancy Test	X	X		[X]	X			X	To be performed for females with childbearing potential only [Only for sites where additional safeguards are required: Supervised urine pregnancy test]
i.v. drug administration (zoledronic acid)		X			X				
Dispense calcium and vitamin D, if required	X	X			X				
DXA measurements (lumbar spine, total body and distal femur)	X				X			X	
X-ray	X							X	Lateral thoraco-lumbar spine and postero-anterior left hand/wrist
Adverse events and SAEs (D)	X	X	X	X	X	X	X	X	SAEs only collected between Visit 8A and Visit 9 (AEs during this time recorded as medical history)
Study completion								X	
S = Source data, D = Database, TD = study treatment discontinuation, PSW = premature patient withdrawal									

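### Section 6.5.4.2 states the Visit 9 creatinine hold in the wrong direction and contradicts exclusion criterion 6

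*Protocol*

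**What the plan says.** Protocol Section 6.5.4.2 schedules a local serum creatinine at Visit 9 (and at Visit 8A for Group 2) to support exclusion. It then gives a mandatory rule: "If local serum creatinine at Visit 9 is less than the normal range, the infusion must not be given". One retest is allowed at the investigator's discretion, and "If the serum creatinine retest is in the normal range, the patient may be dosed".

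Exclusion criterion 6 in Section 4.2 points the other way: "Serum creatinine above the normal range at Visit 9 (Group 1) or an increase between Visit 8 A and Visit 9" of more than 0.5 mg/dL (44.2 µmol/L) for Group 2. Key exclusion 5 in the Protocol Summary agrees, listing "a serum creatinine above the normal range at Visit 9 (Group 1") and the same Group 2 rise.

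Tables 6-1 and 6-2 annotate the local creatinine "For exclusion purposes" and schedule an eligibility check at Visit 9 in both groups. Neither table lists a local creatinine after Visit 9, so the rule governs the first extension infusion only.

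**The concern.** Two binding instructions for the same test at the same visit act on opposite tails. Taken literally, Section 6.5.4.2 withholds drug for a low creatinine, which no exclusion criterion mentions, and sets no hold for a raised one. Section 3.6 names renal injury as the hazard, which makes a high value the one to act on.

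The local Visit 9 result matters because Section 3.1 lets the central eligibility sample be up to 30 days old at the infusion, so the local value may be the more recent one. Section 9.4.1 gives renal safety particular attention.

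The reverse error also has a consequence. A child whose value stayed low on retest would not be dosed and would be a screening failure under Section 6.1. In Group 1 that child would be left out of FAS-1 and SAF-1 (Section 9.1), because both require at least one extension dose. Yet Section 4.2 closes by forbidding investigators to add exclusions, so a site could not follow both sections.

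**Working it through.** There is no planned figure to reproduce. The check traces each rule on example values. The ranges come from Appendix 1, Table 13-1; local laboratory ranges may differ, and the patient values are assumptions.

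**Step 1. The two rules as written.** Girl aged >7-10 years, range 0.2-0.6 mg/dL.

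| Case | Visit 8A | Visit 9 | Criterion 6 | Section 6.5.4.2 |
|---|---|---|---|---|
| a. Group 1 | n/a | 0.9 | excluded (0.9 > 0.6) | no hold |
| b. Group 1 | n/a | 0.15 | not excluded | hold (0.15 < 0.2) |
| c. Group 2 | 0.4 | 0.8 | not excluded (rise 0.4) | no hold |
| d. Group 2 | 0.4 | 1.0 | excluded (rise 0.6) | no hold |

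The rules disagree in a, b and d. Across ages, the literal hold acts below 0.2 mg/dL (age 5-7) up to below 0.5 mg/dL (age >16-20). It never acts above the upper limits of 0.5 to 0.9 mg/dL, where criterion 6 applies to Group 1.

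**Step 2. Is swapping the direction enough?** For Group 1, yes. For Group 2, no: an above-normal hold would stop case c, which criterion 6 allows. It would also miss a child aged >16-20 (range 0.5-0.9) who goes from 0.3 to 0.9. That value is not above range, but the rise is 0.9 − 0.3 = 0.6, which meets criterion 6.

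**Step 3. Is the existing in-range retest release safe for Group 2?** Range widths in mg/dL:

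- Age 5-7: 0.5 − 0.2 = 0.3
- Age >7-10: girls 0.6 − 0.2 = 0.4; boys 0.6 − 0.3 = 0.3
- Age >10-13: 0.7 − 0.3 = 0.4
- Age >13-16: 0.8 − 0.4 = 0.4
- Age >16-20: 0.9 − 0.5 = 0.4

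From an in-range Visit 8A value, an in-range retest is a rise of at most 0.4, within the 0.5 limit. From a below-range Visit 8A value it need not be: the 0.3 to 0.9 child would be released while meeting criterion 6.

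**Step 4. Would a release on the rise alone do?** Starting from the upper limit, it would allow 0.5 + 0.5 = 1.0 mg/dL at age 5-7 (1.0/0.5 = 2.0 times the limit) and 0.9 + 0.5 = 1.4 mg/dL at >16-20 (1.4/0.9 = 1.56 times). That is looser than the present release.

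**Step 5. Both conditions together for Group 2** (retest not above normal, and no more than 0.5 above Visit 8A). The 0.3 to 0.9 child is held, and a retest of 0.9 is refused because the rise is 0.6. In case d, a retest of 0.6 is released (rise 0.2) and a retest of 0.8 is refused (above 0.6). No released child then meets the Visit 9 creatinine part of criterion 6.

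**The case against.** The strongest reply is that this is a drafting slip with little practical effect. The intended rule is stated correctly twice, and the faulty sentence follows directly on a statement that the test serves exclusion. Harm needs staff to follow Section 6.5.4.2 while ignoring Section 4.2 at the same visit. No SAP analysis depends on the sentence. Most of this stands and limits the severity. It does not remove the contradiction, because the sentence is mandatory and is the only place that gives sites a hold-and-retest procedure for this test.

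A reader might go further and infer that children with raised creatinine are left unprotected. The documents do not support that. Criterion 6 is rechecked at Visit 9, an estimated GFR below 60 mL/min/1.73 m² at Visit 8 or 8A excludes, and Section 6.5.4 adds: "An additional lab test for renal monitoring will be performed at Visits 9, 10, 12, 13 and 15". Section 5.6.2 makes renal failure a reason to stop treatment.

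A reader might also defend a low-value hold by pointing to Appendix 1, which marks creatinine outside normal in either direction as notable. That is a flag for reporting, not a dosing or eligibility rule.

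A fair challenge to the repair is that Group 2 hold and release use different standards. A first value of 0.8 after 0.4 is dosed, while 1.0 followed by a retest of 0.8 is refused. That is true. The hold reproduces criterion 6, and the release keeps the upper limit already in Section 6.5.4.2.

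**Conclusion.** Section 6.5.4.2 is wrong as written: its hold acts on low creatinine, whereas criterion 6 and the Protocol Summary act on raised values. The likely source is the neighbouring calcium sentence, judged from the parallel wording only. It is a contradictory dosing instruction that should be corrected, with practical risk reduced by the other renal checks.

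Its size can be given only as thresholds: below 0.2 to below 0.5 mg/dL held, and above 0.5 to above 0.9 mg/dL not held, depending on age. These rest on the Appendix 1 ranges. The documents give no frequency for values below range, or for values that stay low on retest, so neither a number of children lost from FAS-1 and SAF-1 nor a bias in the safety results can be claimed.

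Separately, criterion 6 itself lets a Group 2 child aged 5-7 go from 0.5 to 1.0 mg/dL without exclusion, since the rise does not exceed 0.5. That is the sponsor's stated eligibility rule, and this correction leaves it alone.

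**What to change.** Replace the creatinine hold and retest sentences in Section 6.5.4.2 with a rule by group:

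- **Hold at Visit 9.** Group 1: local creatinine exceeds the upper limit of normal. Group 2: it exceeds the Visit 8A value by more than 0.5 mg/dL (44.2 µmol/L).
- **Retest.** Once, at the investigator's discretion, as now.
- **Release.** Group 1: the retest is not above normal. Group 2: the retest is not above normal and is no more than 0.5 mg/dL above Visit 8A.

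This keeps the existing upper-limit release, removes the hold on low values, and closes the gap for a below-range Visit 8A value. A single above-normal hold for both groups would be simpler, but it would tighten Group 2 eligibility beyond criterion 6 and, used alone, would miss the 0.3 to 0.9 case.

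Cost: a wording change in the next amendment and a clarification letter to sites. Table 6-2 already schedules local creatinine at Visits 8A and 9, so no new samples or visits are needed. The downside is that the Group 2 release is slightly stricter than criterion 6 alone.
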